6.4 Dose Modification / Toxicity Management

Anti-diarrheal and anti-rash medications may be introduced if clinically indicated. Previous Phase I and II studies have demonstrated the frequency and severity of diarrhea can be managed with loperamide. The recommended dose of loperamide is 4 mg at first onset, followed by 2 mg every 2 to 4 hours until diarrhea resolves for 12 hours.

Skin rash or dermatosis has been observed during the first several days of treatment with Tarceva in many patients and has been noted to diminish in severity despite continued treatment. No controlled clinical trials have been conducted to allow definitive recommendations on the treatment of Tarceva -related rash.

Patients who develop a rash characterized by pustules or raised red areas may be treated with oral minocycline (100 mg BID for 7 – 10 days to a maximum of 150 mg BID for 7 – 10 days as clinically indicated) at the discretion of the Investigator. Minocycline is known to interfere with anticoagulants and oral contraceptives. Patients treated with minocycline who are taking anticoagulants and/or oral contraceptives will be instructed to use a second barrier contraceptive while on Minocycline and should be monitored accordingly.

Dose adjustments may be made for toxicity and are to be made based on the greatest degree of toxicity. The initial dose reduction is from 150 mg/day to 100 mg/day. If significant toxicity is still apparent, the dose may be reduced a second time to 50 mg/day. Significant toxicity will be defined as any grade 3 or 4 toxicity that the patient find unbearable. Any patient who fails to tolerate treatment of 50 mg/day will be allowed to have a drug holiday for up to 7 days. Any patient requiring a treatment break longer than seven days may be withdrawn from the study based on the discretion of the principal investigator. Patients may resume drug or increase a previously decrease dosage based on the discretion of their medical oncologist. For analysis and monitoring patients on any dose of drug will be considered “on active treatment”.

Tarceva dosing should be discontinued for any grade 3 or greater toxicity that does not respond to treatment or failure to recover from hematological toxicity within 14 days.

For patients that are off Tarceva for more than 30 days the only toxicities that will be reported and recorded in PDMS will be neurocognitive decline.

7.0 Radiation Therapy

Radiation therapy will be given once per day, five days a week for 14 days. Radiation will be given at a dose of 250 cGy per day for 14 fractions for a total dose of 3500 cGy. Radiation will be delivered with 6MV photons using opposed lateral beams dosed to mid plane.

8.0 Adverse Events

All adverse events will be graded according to NCI CTC version 3.0

Adverse drug experience means any adverse event associated with the use of a drug in humans, whether or not considered drug related, including the following: an adverse event occurring in the course of the use of a drug product in professional practice; an adverse event occurring from drug overdose, whether accidental or intentional; an adverse event occurring from drug abuse; an adverse event occurring from drug withdrawal; and any failure of expected pharmacological action (21 CFR 314.80).

An adverse event is any adverse change from the subject's baseline condition, including any clinically significant laboratory test value abnormality that occurs during the course of the clinical study after the informed consent is signed, whether the adverse event is considered related to the treatment or not.

All adverse events will be collected until one month post last day of Tarceva or radiation (whichever is last). This may require obtaining clinical blood samples for appropriate laboratory tests until their values return to baseline levels or performing follow-up physical examinations until resolution of identified abnormalities.

The most common adverse reactions in patients receiving single-agent TARCEVA 150 mg were rash and diarrhea. Grade 3/4 rash and diarrhea occurred in 9% and 6%, respectively, in TARCEVA-treated patients. Rash and diarrhea each resulted in study discontinuation in 1% of TARCEVA-treated patients. Six percent and 1% of patients needed dose reduction for rash and diarrhea, respectively. The median time to onset of rash was 8 days, and the median time to onset of diarrhea was 12 days.

	TARCEVA 150 mg N = 485			Placebo N = 242		
NCI CTC Grade	Any Grade	Grade 3	Grade 4	Any Grade	Grade 3	Grade 4
MedDRA Preferred Term	%	%	%	%	%	%
Rash	75	8	<1	17	0	0
Diarrhea	54	6	<1	18	<1	0
Anorexia	52	8	1	38	5	<1
Fatigue	52	14	4	45	16	4
Dyspnea	41	17	11	35	15	11
Cough	33	4	0	29	2	0
Nausea	33	3	0	24	2	0
Infection	24	4	0	15	2	0
Vomiting	23	2	<1	19	2	0
Stomatitis	17	<1	0	3	0	0
Pruritus	13	<1	0	5	0	0
Dry skin	12	0	0	4	0	0
Conjunctivitis	12	<1	0	2	<1	0
Keratoconjunctivitis sicca	12	0	0	3	0	0
Abdominal pain	11	2	<1	7	1	<1

Rare, But Serious

In some patients taking erlotinib and oral blood thinners INR have been reported abnormally elevated. The elevation of INR was associated with bleeding.

- Some patients (less than 1%) taking erlotinib can get 'interstitial lung disorder' or 'interstitial pneumonia'. This can cause worsening of existing lung problems or causes new lung problems, such as sudden onset of shortness of breath, fever, cough, and/or problems

with oxygen getting through the lungs to the blood. In some patients, this lung disease has been fatal.

- Inflammation of the lung, pulmonary fibrosis (scarring), and lung infiltrates may occur in patients on erlotinib.
- Eye changes and blurred vision and corneal (lining of the eye) damage
- Stroke
- Blood clots
- Weight loss
- Confusion
- Heart attack

Serious side effects of erlotinib are infrequent. They are usually not severe enough to require discontinuing treatment.

PDMS Recording Requirements

AE's will be recorded according to Phase II protocols.

Recommended Adverse Event Recording (PDMS) Guidelines					
Attribution	Grade 1	Grade 2	Grade 3	Grade 4	Grade 5
Unrelated	Phase I	Phase I	Phase I Phase II	Phase I Phase II Phase III	Phase I Phase II Phase III
Unlikely	Phase I	Phase I	Phase I Phase II	Phase I Phase II Phase III	Phase I Phase II Phase III
Possible	Phase I Phase II	Phase I Phase II Phase III	Phase I Phase II Phase III	Phase I Phase II Phase III	Phase I Phase II Phase III
Probable	Phase I Phase II	Phase I Phase II Phase III	Phase I Phase II Phase III	Phase I Phase II Phase III	Phase I Phase II Phase III
Definitive	Phase I Phase II	Phase I Phase II Phase III	Phase I Phase II Phase III	Phase I Phase II Phase III	Phase I Phase II Phase III

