2.0 Study Objectives

2.1 Primary Endpoints:

To determine if Tarceva, given orally on a daily basis along with concurrent whole brain radiation therapy **improves median survival** of patients with brain metastases, compared with historical controls.

[figure not shown]
2.2 Secondary Endpoints:

- 2.2.1 To see if Tarceva along with concurrent WBRT, improves **quality of life** as assessed with the Spitzer Quality of Life Index (Appendix E) and the Folstein Mini-Mental Status Exam (Appendix F). Optional test will include Digit Span, Digit Symbol, Hopkins Verbal Learning Test, Controlled Oral Word Association, Trail Making Test Part A, Trail Making Test Part B, Grooved Pegboard, Barthel [name]. Anderson Symptom Inventory, and Functional Assessment of Cancer Therapy with Brain Module. As of July 18, 2012- Optional tests will no longer be completed.
- 2.2.2 To see if Tarceva along with concurrent WBRT, influences cause of death compared to matched controls, based on key attributes such as stage, age KPS, number of brain metastasis, etc.
- 2.2.3 To see if Tarceva along with concurrent WBRT, increases time to progression of disease.
- 2.2.4 To sequence the EGFR receptor of patients treated with Tarceva, in order to identify specific gene mutations that may correlate with favorable responses to Tarceva.
- 2.2.5 To study downstream proteins involved in the EGFR cascade such as p-EGFR, Raf, PKC, JNK, and p-AKT. This information will be combined with other protein markers such as E cadherin that appear to increase the probability of response, in the hopes of developing a genetic signature of patients most likely to benefit from this regimen.
- 2.2.6 To confirm the safety profile of Tarceva along with concurrent external beam radiation therapy, in the context of treating central nervous system malignancies.
- 2.2.7 To provide evidence to support a much larger multi-institutional study.

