9.0 Data Collection, Study Monitoring, and Data Disclosure

9.1 Data Collection and Reporting

Data for each patient will be recorded in PDMS.

10. Administrative Considerations

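### All adverse events are to be collected, but the PDMS rule leaves out grade 1-2 events rated Unrelated or Unlikely, so recorded low-grade and any-grade rates depend on investigator attribution

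*Combined protocol and SAP*

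**What the plan says.** Section 8.0 of the protocol defines an adverse event from signed consent onward, "whether the adverse event is considered related to the treatment or not". On collection it says: "All adverse events will be collected until one month post last day of Tarceva or radiation (whichever is last". Footnote g to the study calendar (section 6.0) gives the same rule with much the same window.

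Under PDMS Recording Requirements, at the end of section 8.0, the plan says "AE's will be recorded according to Phase II protocols". The table below that sentence, headed "Recommended Adverse Event Recording (PDMS) Guidelines", crosses five attribution ratings with five grades. Read across grades 1, 2 and 3, its first two rows are "Unrelated Phase I Phase I Phase I Phase II" and "Unlikely Phase I Phase I Phase I Phase II", so for both ratings Phase II first appears at grade 3. The Possible, Probable and Definitive rows include Phase II from grade 1.

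Section 9.1 adds: "Data for each patient will be recorded in PDMS". Objective 2.2.6 is "To confirm the safety profile of Tarceva along with concurrent external beam radiation therapy, in the context of treating central nervous system malignancies". Section 11.5.2 has toxicities summarised by frequency and severity in the six-monthly reports. Section 8.2 has serious adverse events reported whatever their attribution.

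**The concern.** One rule takes in every event. The other keeps low-grade events out of the named database when the investigator thinks treatment was probably not the cause. The plan does not say how the two fit together or where the events left out of PDMS are held.

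This matters because objective 2.2.6 is about the safety of a combination in patients whose disease can produce the same symptoms. Section 8.0 lists confusion among the rare but serious erlotinib events, and brain metastases or whole brain radiation could also explain it. There is no control arm against which to check such a judgement, no blinding is described, and the table does not say whether attribution is to Tarceva, to radiation or to both. Two investigators seeing the same patients could therefore produce different recorded grade 1-2 rates. The optional neurocognitive tests and the MMSE and Spitzer assessments have been discontinued (sections 2.2.1 and 6.3), which leaves more of the neurocognitive safety picture to adverse event recording.

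**Working it through.** **Step 1: which cells are left out.** The table has 5 × 5 = 25 cells. Phase II is missing from 2 ratings (Unrelated, Unlikely) × 2 grades (1, 2) = 4 cells. All 5 × 3 = 15 cells at grades 3 to 5 include Phase II, as do the 3 × 2 = 6 cells for Possible, Probable and Definitive at grades 1 and 2. In total 15 + 6 = 21 cells are recorded and 4 are not.

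**Step 2: whether collecting and recording are separate processes.** Section 8.0 uses one word for collection and another for PDMS entry, so they could be. Two other places suggest they are not. Footnote g says that after the collection window only neurocognitive decline is captured. Section 6.4 states essentially the same cut-off as a limit on what is reported and recorded in PDMS. Read together, they describe one process. The plan nowhere settles the question.

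**Step 3: possible size.** The plan states no figure to reproduce. For scale I use the Tarceva column of the reference table in section 8.0. Let A be the any-grade rate, G3 and G4 the grade 3 and grade 4 rates, and assume that each patient is counted once, at worst grade. Then

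L = A − G3 − G4 (grade 1-2 rate)

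R(q) = A − q × L (recorded any-grade rate)

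Here q is the share of patients with a grade 1-2 event whose events are all rated Unrelated or Unlikely. The documents do not give q, so it is an assumption, shown over its whole range.

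| Event | A | G3 + G4 | L | R(0) | R(0.5) | R(1) |
|---|---|---|---|---|---|---|
| Fatigue | 52% | 14 + 4 = 18% | 34% | 52% | 35% | 18% |
| Anorexia | 52% | 8 + 1 = 9% | 43% | 52% | 30.5% | 9% |
| Nausea | 33% | 3 + 0 = 3% | 30% | 33% | 18% | 3% |
| Cough | 33% | 4 + 0 = 4% | 29% | 33% | 18.5% | 4% |

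In 20 patients, recorded fatigue would run from 20 × 0.52 = 10.4 cases down to 20 × 0.18 = 3.6. Grade 3-4 fatigue is 18% at every q. Grade 1-2 fatigue on placebo in the same table is 45 − 16 − 4 = 25%, so low-grade events that could be rated Unrelated are common in the background.

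**Step 4: with everything entered.** No cell is omitted, and R = A whatever the attribution. Grade 3-5 rates do not change.

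**The case against.** The best defence is that the two rules can both be followed. Every event can be elicited and kept in source records while only some are entered in PDMS. Section 6.1 mentions a Case Report Form, and section 5.6 mentions progress notes and the patient record. Leaving low-grade, unrelated events out of the database is also a deliberate, phase-specific rule that the protocol adopts openly. This defence stands in part: there is no strict contradiction, and the documents do not show that events are lost. But section 6.1 ties the Case Report Form to concomitant treatment only, and the plan never names where unentered events go or how they would reach a safety summary.

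A reader might infer four stronger things, and the documents support none of them.

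- That toxicity rates in general depend on attribution. Every grade 3-5 event is recorded, and so is every grade 1-2 event rated Possible or higher.
- That the low ends of the ranges are likely values. They need every grade 1-2 event to be rated Unrelated or Unlikely. Fatigue, anorexia, nausea and cough all appear in the protocol's own Tarceva table, so a rating of Possible is quite plausible.
- That an event put down to radiation alone would be dropped. Section 8.0 speaks of relation to the treatment, and objective 2.2.6 concerns the combination, so such an event may well count as related. The plan is silent.
- That a comparison with the 485 versus 242 patient table is spoiled. None is planned. The external comparisons in section 11.5.1.1 concern survival, CNS progression-free survival and cause of death.

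**Conclusion.** The concern holds as an unreconciled gap with a limited but real effect. Collection is stated without limit, entry in the named database is filtered by attribution at grades 1 and 2, and the plan does not connect the two. Recorded grade 1-2 and any-grade rates for a secondary safety objective therefore depend on a judgement that a single-arm trial cannot check. The survival endpoint, grade 3-5 rates and serious adverse event reporting are untouched.

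For fatigue, the recorded any-grade rate could lie anywhere between 18% and 52% with the same true toxicity. These are logical bounds, not estimates. They rest on an unknown q and on single-agent reference rates that may not apply to patients having whole brain radiation. The direction is certain only in that filtering cannot raise a recorded rate; how far it lowers one is unknown. This is a cheap improvement worth making, not a flaw that undermines the trial.

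**What to change.** 1. Enter in PDMS all adverse events of any grade and attribution over the full section 8.0 window: from signed consent to one month after the last Tarceva dose or radiation, whichever comes later. Say explicitly that collection means entry in PDMS.
2. State that attribution covers both treatments, and record it separately for Tarceva and for radiation.
3. Report all-cause rates by grade as the main safety table, with attributed rates alongside.
4. If the filter is kept for any period, such as later Tarceva maintenance, amend section 8.0 and footnote g to say so, and label grade 1-2 rates from that period as at least possibly related.
5. Report low-grade rates by centre. The Arizona data are to be combined with these, and the recording rule used there is not given. A change at one centre could make the low-grade data differ.

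The cost is modest extra data entry for about 20 patients, for events that staff already elicit at the adverse event checks in the study calendar. It grows with time on Tarceva, which is the main reason the sponsor might choose the fourth item for the maintenance period.

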8.1 Severity of Adverse Drug Experiences

Adverse drug experiences will be graded according to the criteria in the National Cancer Institute (NCI) Common Terminology Criteria for Adverse Events (CTCAE) version 3.0

(Appendix B). The toxicity criteria can be accessed through the NCI website (ctep.cancer.gov/reporting/ctc.html).

Clinical adverse events not classified by this scale will be categorized using the following definitions:

MILD	discomfort noted, but no disruption of normal daily activity
MODERATE	discomfort noted of sufficient severity to reduce or adversely affect normal activity
SEVERE	incapacitating, with inability to work or perform normal daily activity

8.2 Serious Adverse Event Reporting (SAE)

A serious adverse event is – any adverse drug experience occurring at any dose that results in any of the following outcomes:

- Death
- A life-threatening adverse drug experience – any adverse experience that places the patient, in the view of the initial reporter, at immediate risk of death from the adverse experience as it occurred. It does not include an adverse experience that, had it occurred in a more severe form, might have caused death.
- Inpatient hospitalization or prolongation of existing hospitalization
- A persistent or significant disability/incapacity – a substantial disruption of a person's ability to conduct normal life functions.
- A congenital anomaly/birth defect.

Important medical events that may not result in death, be life-threatening, or require hospitalization may be considered a serious adverse drug experience when, based upon appropriate medical judgment, they may jeopardize the patient or subject and may require medical or surgical intervention to prevent one of the outcomes listed in this definition. Examples of such medical events include allergic bronchospasm requiring intensive treatment in an emergency room or at home, blood dyscrasias or convulsions that do not result in inpatient hospitalization, or the development of drug dependency or drug abuse (21 CFR 312.32).

- Important medical events as defined above may also be considered serious adverse events. Any important medical event can and should be reported as an

SAE if deemed appropriate by the Principal Investigator or MDACC- Office of Research Education and Regulatory Management (ORERM).

- All events occurring during the conduct of a protocol and meeting the definition of a SAE must be reported to the IRB in accordance with the timeframes and procedures outlined in “University of Texas M. D. Anderson Cancer Center Institutional Review Board Policy on Reporting Serious Adverse Events”. Unless stated otherwise in the protocol, all SAEs, expected or unexpected, must be reported to ORERM, regardless of attribution (within 5 working days of knowledge of the event).
- All life-threatening or fatal events, expected or unexpected, and regardless of attribution to the study drug, must have a written report submitted within 24 hours (next working day) of knowledge of the event to the Safety Project Manager in ORERM.
- The MDACC “Internal SAE Report Form for Prompt Reporting” will be used for reporting to ORERM.
- Serious adverse events will be captured from the time the patient signs consent until 30 days after the last dose of study treatment. Serious adverse events must be followed until clinical recovery is complete and laboratory test have returned to baseline, progression of the event has stabilized, or there has been acceptable resolution of the event.
- Additionally, any serious adverse events that occur after the 30 day time period that are related to the study treatment must be reported to ORERM. This may include the development of a secondary malignancy.

Reporting to FDA:

- Serious adverse events will be forwarded to FDA by MDACC (Safety Project Manager ORERM) according to 21 CFR 312.32.

It is the responsibility of the PI and the research team to ensure serious adverse events are reported according to the Code of Federal Regulations, Good Clinical Practices, the protocol guidelines, MDACC’s guidelines, and Institutional Review Board policy.

8.3 Investigator Communication with Supporting Companies

The MDACC “Internal SAE Report Form for Prompt Reporting” will be used for all SAEs, and all SAEs will be faxed (within 24 hours of learning of the event) to:

OSI Drug Safety
[contact]

9.0 Data Collection, Study Monitoring, and Data Disclosure

9.1 Data Collection and Reporting

Data for each patient will be recorded in PDMS.

10. Administrative Considerations

10.1 Patient Registration Procedure

All subjects will be registered in Clinical Oncology Research System (CORe).

11.0 Statistical Consideration

Phase II study of 20 patients (40 in total when combined with the Arizona study) to determine the effect of combining whole brain radiation with Tarceva. From what has been observed from the initial 15 patients enrolled at the Arizona Cancer Center, we would expect the vast majority of patients, to be in recursive partitioning analysis (RPA) class II, with the remaining falling into class I and a small percentage in class III. From the first 15 patients enrolled 4 remain alive, of the patients that passed away the median survival has been 9.5 months, while the RPA predicted survival was 4.2 months. While the initial result from the Arizona study are encouraging accrual has been longer than expected, which is why we have proposed to open a similar study here at MD Anderson. If this initial phase II study is successful it will serve as the foundation for a much larger multi-institutional phase III study.

11.1 Study Endpoints

Primary Endpoint:
Median survival

11.2 Background

The primary objective of this study is to estimate the median survival of patients with brain metastases from non-small cell lung cancer treated with Tarceva combined with whole brain radiation therapy.

Gaspar et al. provides a definition of average survival for patients with brain metastases stratified into three classes based on age, KPS and control of primary disease. This information came from an analysis of 1200 patients from three earlier RTOG trials. Based on this study one can expect the following survival. (9)

Class 1 patients with KPS >70 and age <65yrs to live approximately 7.1 months
Class 2 patients not meeting Class 1 or 3 criteria, have an average survival of 4.2 months
Class 3 patients with KPS < 70 have an average survival of 2.3 months

This study will be conducted in parallel with an identical study at the University of Arizona that was started on March of 2006. So far this study has accrued 15 of 20 patients, as of 8/2008. From these initial 15 patients the vast majority fall into RPA class II, with the reaming falling into class I and a small percentage in class III. From the first 15 patients enrolled the 4 remain alive, of the patient that have passed away the median survival has been 9.5 months, while the RPA predicted survival was 4.2 months.

The data from the Arizona study will be combined with this study (based at MD Anderson) which will accrue an additional 20 patients, producing a total of 40 patients for analysis. Patients will be analyzed based on the intent-to-treat principle. We will also analyze the subset of evaluable patients. Evaluable patients are defined as those patients that have completed WBRT and Tarceva.

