11.3 Sample Size

We assume that the true median survival for the historical control is 4.2 months (averaging to the historical value for class 2), and we assume that the true median survival will be increased by 43% to 6.0 months with this therapeutic approach. This represents a hazard ratio (experimental/historical) of 0.70. We assume uniform accrual over 24 months, an additional follow-up period of 9 months, exponentially distributed death times. The exponential MLE test for a single arm study at the one-sided 0.10 significance level will yield 80% power to detect an increase in median survival from 4.2 to 6 months with a sample size of 40 patients.

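### The 0.10 level and 80% power in section 11.3 assume 40 unobserved patients; 15 already had known outcomes, and no comparison with 4.2 months is planned in the patients still to be enrolled

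*Combined protocol and SAP*

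**What the plan says.** - Section 2.1 sets the aim as improved median survival in "patients with brain metastases, compared with historical controls". Section 11.2 words it as estimation: "The primary objective of this study is to estimate the median survival of patients with brain metastases" from NSCLC treated with the combination.
- Section 11.2 reports on the Arizona study: "So far this study has accrued 15 of 20 patients, as of 8/2008". It then states that "The data from the Arizona study will be combined with this study", 20 patients from each centre.
- Section 11.0 gives the outcomes so far: "From the first 15 patients enrolled 4 remain alive, of the patients that passed away the median survival has been 9.5 months", against a predicted 4.2 months. It adds: "While the initial result from the Arizona study are encouraging accrual has been longer than expected", and gives the slow accrual as the reason for opening MD Anderson.
- Section 11.3: "The exponential MLE test for a single arm study at the one-sided 0.10 significance level will yield 80% power" to detect a rise from 4.2 to 6 months with 40 patients, under uniform accrual over 24 months and 9 further months of follow-up. It does not mention that part of the sample has been observed.
- Section 11.5.1.1 plans a Kaplan-Meier median with 95% CI in all patients, Kaplan-Meier by institution and class, an MD Anderson to Arizona hazard ratio, and comparison and matched-pair testing against RTOG 0118. The exponential test and the 4.2-month reference do not appear there.

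**The concern.** A level and a power describe a test before its data are seen. Here 15 of the 40 patients had been seen when the plan was written, and the result had been called encouraging. From that point the chance that the pooled test rejects depends partly on a fixed, known contribution, so 10% and 80% no longer tell the reader how likely a false or a true positive is.

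This matters because of what follows from a positive result: "If this initial phase II study is successful it will serve as the foundation for a much larger multi-institutional phase III study". A phase III decision needs to know how much support comes from patients who were not part of the reason for optimism. The MD Anderson stratum shows 20 of the 25 new patients, but only as an estimate. The other 5 cannot be told apart from the first 15 Arizona patients in any planned analysis.

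**Working it through.** **Inputs.** Null median 4.2 months, alternative 6.0, one-sided 0.10 (z = 1.2816), 24 months of accrual plus 9 of follow-up, N = 40 (section 11.3). First 15 patients: 4 alive, so 15 − 4 = 11 dead if none were lost; median among the dead 9.5 months (section 11.0). Still to enrol: 20 MD Anderson + 5 Arizona = 25 (section 11.2).

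**1. The plan's own figure.** With λ = ln 2 / median, A = 24 and F = 9, the probability of death on study is 1 − [exp(−λF) − exp(−λ(A+F))]/(λA) = 0.880 at a 6.0-month median, or 35.2 deaths among 40. Power = Φ(ln(6/4.2) × √35.2 − 1.2816) = Φ(0.835) = 79.8%. The stated 80% is reproduced. Simulating the log-hazard form of the test with all 40 unobserved gives a level of about 0.085.

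**2. Share already observed.** 11 / 35.2 = 31% of the expected deaths.

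**3. Possible Arizona exposure.** The documents do not give it.
- Floor: six of the 11 deaths at 9.5 months or later, all other time zero: 6 × 9.5 = 57 person-months.
- Ceiling, with 29 months between March 2006 and 8/2008: 6 × 9.5 + 5 × 29 + 4 × 29 = 318.
- One reference value: 11 deaths averaging 9.5 months, survivors' time ignored: 11 × 9.5 = 104.5.

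**4. The pooled test given the first 15.** It rejects if ln(λ₀/λ̂) × √deaths > 1.2816, where λ₀ = ln 2/4.2. The 11 deaths and the exposure are held fixed. The 25 new patients are simulated under 24 + 9 months, and the 4 survivors are followed for a further 14 months (assumed).

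| Arizona exposure (person-months, assumed) | Rejects, true median 4.2 | Rejects, true median 6.0 | Under 4.2: pooled rejects, new 25 alone do not |
|---|---|---|---|
| 57 | 3% | 52% | 0.2% |
| 78 | 10% | 72% | 3% |
| 104.5 | 30% | 90% | 22% |
| 120 | 48% | 96% | 40% |
| 160 | 90% | 99.8% | 82% |

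Break-even with 10% is near 78 person-months. Above 160 the null rejection rate climbs further. With 5 + 9 months for the 25, the null column is 3%, 10%, 32%, 50% and 91%.

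**5. What the new patients must show.** The 25 alone need an estimated median of 4.2 × exp(1.2816/√22.0) = 5.5 months to reject. At 104.5 person-months from the first 15, about 4.65 months in the 25 is enough for the pooled test to reject.

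**6. Power in the 25.**
- 24 + 9 months: 22.0 deaths; Φ(0.3567 × √22.0 − 1.2816) = 65% (64% by simulation).
- 5 + 9 months (upper end of section 11.4, assumed also for the 5 Arizona patients): 18.3 deaths, 60%.

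**The case against.** The strongest reply is that 0.10 and 80% are unconditional figures, and correct ones. Any test's conditional rejection chance moves once some outcomes are known; that is not in itself type I error inflation. Two-stage designs with a futility stop pool first-stage patients in the same way. If MD Anderson had opened only because Arizona looked good, the overall chance of opening and then falsely rejecting would fall: a simulation assuming 15 patients accrued over 29 months gives 0.084 with no gate and 0.072 if opening required an interim estimate above 4.2 months. This stands. A reader might infer from sections 11.0 and 11.3 that the error rate is inflated, or that the 6.0-month target or the 0.10 level was picked from the Arizona results. The documents support neither: they attribute the second site to slow accrual. Equally, they document no pooling rule that predates the Arizona outcomes.

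It can also be said that the overlap is disclosed just before section 11.3, that the stated objective is estimation, and that survival by institution is planned. All true. But section 2.1 asks for a comparison with historical controls, section 11.3 sizes the study by a test, and the institution split neither compares new patients with 4.2 months nor isolates the 5 later Arizona patients.

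Finally, requiring the new-patient test to govern would raise the false-negative risk from 20% to 35-40%. The text also carries edits dated 2012 and 2013, so an analysis added now may itself follow the data. These are good reasons to make the addition a sensitivity analysis.

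**Conclusion.** The point holds in a limited form. Section 11.3 should not present 0.10 and 80% without saying that they assume 40 unobserved patients, and the plan lacks a separate look at the patients enrolled after 8/2008.

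The size is not determined. Over the exposures tabulated, the pooled test's conditional null rejection rate runs from 3% to 90%, on either side of 10%, and the documents do not say where the trial lies. The figures rest on exponential survival, no loss to follow-up among the 15, 14 further months for the survivors, and the log-hazard form of the test. The plan does not define the form: a chi-square version gives levels of 0.102 (40 patients) and 0.103 (25), and 68% power in the 25. The figures do not apply to the RTOG 0118 matched-pair test.

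A reader might also infer that a positive pooled result would rest mainly on deaths already seen. That is too strong: the 15 supply 31% of expected deaths and, at 104.5 person-months, about 37% of the exposure at the rejection threshold. Whether the new-patient test should replace the pooled one as the governing test is a design choice on which statisticians would differ; it is not required here.

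**What to change.** 1. In section 11.3, state that 0.10 and 80% are unconditional planning figures for 40 unobserved patients and do not hold given the Arizona data known by 8/2008.
2. In section 11.5.1.1, keep the pooled 40-patient Kaplan-Meier median with its 95% CI. Add, as a named sensitivity analysis, the Kaplan-Meier median with CI and the one-sided 0.10 exponential test against 4.2 months in the patients enrolled after 8/2008 (20 MD Anderson plus 5 Arizona). Report it beside the pooled result when success is judged for phase III.
3. State the power of that analysis: about 65% under 24 + 9 months, or about 60% with 5-month accrual and 9 months of follow-up.

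The cost is one extra analysis, a few sentences, and a less favourable stated power for the independent evidence. No patients are added.
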